Efficacy Evaluations	
Primary outcome – Psychological - Least means change from baseline scores at mid-treatment, post-treatment, and follow-up on positive emotions (mDES), role functioning (QLS, FESFS), and stress reactivity (PSS, DSI).
 
Primary outcomes – Biological - Least means change from baseline to post-treatment on salivary cortisol.
 
Secondary outcomes- Psychological- Least means change from baseline scores at mid-treatment, post-treatment, and follow-up on psychiatric symptoms (PANSS), mindfulness (FFMQ, short SCS), and well-being (PWB).

	
Secondary outcomes- Biological- Least means change from baseline to post-treatment on resting/baseline heart rate variability (RSA).

Safety Evaluations	
A safety plan for the intervention sessions will be developed prior to the initiation of the study with [name], as well as the study clinicians.

Statistical and Analytic Plan	
Analyses will focus on average change over time (i.e., change from baseline scores) on primary outcomes (positive emotions, role functioning, stress reactivity, salivary cortisol) and secondary outcomes (psychiatric symptoms, mindfulness, well-being, heart rate variability). Analyses will utilize hierarchical linear models with random intercepts for each subject that will estimate the average change from baseline (i.e., least means change) for each treatment group (TAU, I-CAT) at mid-treatment, post-treatment, and follow-up timepoints.

DATA AND SAFETY MONITORING PLAN	
[name] will function as the Project Medical Officer. An independent physician will serve as the Medical Monitor ([name], from the Department of Psychiatry).

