2 RESEARCH DESIGN AND METHODS

2.1 OVERVIEW

To test the feasibility of a clinical trial implementing I-CAT for people with first-episode schizophrenia, a small RCT with 40 individuals (20 assigned to I-CAT and 20 to TAU) will be conducted. The objective of this small RCT is to conduct a feasibility trial of the I-CAT approach in anticipation of a larger scale trial. To complete this object, we will conduct a study using a small RCT comparing I-CAT to TAU (i.e., supportive therapy). This will allow us to evaluate the feasibility of recruitment, randomization, retention, assessment procedures, and the training and implementation of the revised I-CAT manual in a real-world setting. Successful completion of this stage of treatment development will provide preliminary information on the possible impact of I-CAT on stress reactivity.

Justification and Feasibility - The proposed study will evaluate the outcomes of the I-CAT intervention in a real-world clinical setting to estimate effect sizes in preparation for a larger clinical trial. We will begin standardizing the intervention, refine the clinician training protocol, and a measure of fidelity. The goal is to establish estimates of effect size before moving forward with a large-scale RCT. We are confident that comparing I-CAT to an active treatment will establish an accurate estimate of effect size from our key outcome domains.

Sample Size Justification - We have chosen to collect data from a sample size of 40 subjects with 20 in

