each group. Currently, OASIS has a census of 140 people and admits approximately 3-5 people per month. With approximately 2 years to recruit 40 subjects, we will have to recruit approximately two subjects per month. In a previous randomized treatment trial at OASIS, we recruited 45 people with schizophrenia in approximately 30 months, suggesting these recruitment goals are realistic. 48 We conducted a power analysis using the Optimal Design power software developed by Raudenbush. The results suggest that, with 20 subjects per group, $\alpha=.05$, and covariates that account for 40% of the variance, the study should have reasonable power ($B = .70$) to reliably detect treatment effect sizes of .65 or larger (although in this proposal, we have not designed the study with the anticipation that we will see effect sizes of this magnitude). We will compute effect sizes from these analyses and regard them as clinically meaningful if they exceed .20 for more distal outcomes and .30 for more proximal outcomes.

Research Design - We will randomly assign 40 subjects to either I-CAT or ($n=20$) or TAU ($n=20$) for up to nine-months of individual therapy sessions. Blinded raters will assess subjects at mid-treatment, post-treatment, and follow-up. A computer program, held by the data manager, will determine randomization; randomization sequences will not be known by anyone in advance. The data manager will then do the randomization. Subjects will be instructed not to discuss the type of therapy they are receiving with the blinded research assistants. Any violations to treatment blinding will be noted in the study log and possibly addressed in subsequent data analyses.

Biological Specimen Analyses - Our primary outcome measure is cortisol. Our preferred method of analyzing cortisol will be collecting saliva at 5 times points over 2.5 hours and performing analyses with the Salimetrics High Sensitivity assay.

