5 STATISTICAL ANALYSES

5.1 DATA ANALYTIC PLAN

Feasibility will be defined by our ability to meet our recruitment targets (40 people), frequency of engagement in the intervention by participants (session attendance and attrition rates), and feedback on the intervention from I-CAT participants.

Differences between group demographics to check effectiveness of randomization will utilize independent samples t-tests (continuous variables) or Pearson chi-square tests (categorical variables). Little's Missing Completely at Random test will be performed to establish whether data is missing at random and to determine if data imputation will be needed for subsequent analyses.

To test whether intervention groups differ in their amount of change on treatment outcomes over time, data will be analyzed according to the intent-to-treat principle, in which all subjects randomized will be included in the analysis. To examine intervention effects on primary and secondary outcomes, linear mixed-effects models will be utilized with restricted maximum likelihood estimation where missing data will be handled via full information maximum likelihood. The linear mixed-effects models will include effects of time (i.e., baseline, mid-treatment, post-treatment, and follow-up), intervention group, and a group by intervention interaction with random intercepts to account for baseline differences on outcome variables. Observations classified as outliers (i.e., residual values less than or greater than 1% of all observations) will be excluded. Changes from baseline will be estimated using least-squares means for each intervention group.

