5.2 POWER ANALYSIS

We conducted a power analysis using the Optimal Design power software developed by Raudenbush. The results suggest that, with 20 subjects per group, $\alpha = .05$, and covariates that account for 40% of the variance, the study should have reasonable power ($B = .70$) to reliably detect treatment effect sizes of .65 or larger (although in this proposal, we have not designed the study with the anticipation that we will see effect sizes of this magnitude). We will compute effect sizes from these analyses and regard them as clinically meaningful if they exceed .20 for more distal outcomes and .30 for more proximal outcomes.

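### Section 5.1 deletes observations by the size of their model residual and plans no all-data analysis, so intervals and tests for the four-visit outcomes are too optimistic

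*Combined protocol and SAP*

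**What the plan says.** Section 5.1 plans linear mixed-effects models, fitted by REML with random intercepts, for all primary and secondary outcomes. It then states: "Observations classified as outliers (i.e., residual values less than or greater than 1% of all observations) will be excluded". The sentence does not say:

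- whether 1% applies to each tail or in total, or which percentile definition is used;
- whether residuals are conditional (distance from the subject's own predicted level) or marginal (distance from the group-by-visit mean);
- whether deletion is done once or repeated.

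No sensitivity analysis is mentioned anywhere. The same paragraph commits to the "intent-to-treat principle, in which all subjects randomized will be included in the analysis".

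The Synopsis (Efficacy Evaluations) gives the psychological primary outcomes as "Least means change from baseline scores at mid-treatment, post-treatment, and follow-up on positive emotions (mDES), role functioning (QLS, FESFS), and stress reactivity (PSS, DSI"), which with baseline makes four visits. The biological outcomes have two visits: "Least means change from baseline to post-treatment on salivary cortisol", and "Least means change from baseline to post-treatment on resting/baseline heart rate variability (RSA").

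On purpose, Section 2.1 says "The goal is to establish estimates of effect size before moving forward with a large-scale RCT". Section 5.2 adds "We will compute effect sizes from these analyses and regard them as clinically meaningful if they exceed .20 for more distal outcomes", with .30 for more proximal ones.

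**The concern.** A percentile rule finds outliers in every dataset, however clean, because some residuals are always the largest. Most psychological outcomes here are bounded scales (mDES 0–4, PSS 0–40, QLS 0–42), so an in-range score is not an error merely because the model fits it badly. Removing the most extreme residuals and refitting as if the remainder were the whole sample understates the residual variance.

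At stake are the confidence intervals, the between-group tests and possibly the standardized effect sizes. Section 5.2 takes the effect sizes from these same analyses, so they carry forward into planning the larger trial. The open choices also change the result and could be settled after the data are seen.

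**Working it through.** **The plan's own figure.** The plan gives no figure for this rule. Its one computed figure is power of .70 at an effect of .65, with 20 per arm and covariates explaining 40% of variance. Recalculated: .65/√0.6 = 0.839; 0.839 × √(20/2) = 2.65; Φ(2.65 − 1.96) ≈ 0.756, or 0.734 with the noncentral t. That mismatch is separate and does not affect this point.

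**Inputs from the documents.** 20 per arm; four visits; α = .05; random-intercept REML model with group, time and their interaction (Section 5.1's interaction term is read as group by time).

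**Assumed inputs.** Two-sided tests; total SD 1; intraclass correlation (ICC) 0.3–0.7; normal, t or log-normal errors; 0–20% missing; one delete-and-refit pass.

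**Step 1: values deleted at 1% per tail.** Complete data give 40 × 4 = 160 observations.

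- Linear interpolation: 159 × 0.01 = 1.59, so the cut lies between the 2nd and 3rd smallest residuals. Two go per tail, four in all.
- (n+1)p definition: 161 × 0.01 = 1.61, so the cut lies between the 1st and 2nd. One goes per tail, two in all.

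Across nine standard definitions the total is 2 (five definitions), 3 (two) or 4 (two). Taking 1% in total also removes 2.

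**Step 2: hand check of the mechanism** (normal errors, four deleted).

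- The share removed is 4/160 = 2.5%, which puts the cut at k = 2.241 SD, where the normal density is 0.0324.
- The residual variance left is (0.975 − 2 × 2.241 × 0.0324)/0.975 = 0.851, so the standard error is multiplied by √0.851 = 0.923.
- With ICC 0.63, the full-data standard error of the group difference in change is √(4 × 0.37/20) = 0.272. Trimmed, it is 0.923 × 0.272 = 0.251. The simulated values are 0.271 and 0.250.
- This alone turns a 5% test into about 7%.
- With normal errors the trimmed estimate is also more variable. A large-sample approximation, with d = 2 × 2.241 × 0.0324/0.975 = 0.149, gives a variance factor of (1/0.975 + 0.149)² × 0.830 + 0.149² × 0.170 = 1.148, an SD factor of 1.072.
- The ratio of reported to true standard error is then 0.923/1.072 = 0.861. The critical value 1.98 acts like 1.71, an error rate of about 9%.

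**Step 3: simulation under no effect** (four visits, normal errors, complete data, ICC 0.5–0.63; 10,000 trials per scenario).

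| Rule | Residual | Contrast | Interaction F |
|---|---|---|---|
| All data kept | – | 5.0% | 4.8–5.6% |
| 2 deleted | conditional | 7.3–8.0% | 8.8–10.4% |
| 2 deleted | marginal | 6.2–6.4% | 7.1–7.4% |
| 4 deleted | conditional | 9.3–9.5% | 12.1–13.1% |
| 4 deleted | marginal | 7.2–7.5% | 8.8–9.1% |
| Cut-off at 2.33 or 2.58 model SDs | either | 5.7–6.9% | 6.3–8.6% |

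Coverage of the 95% interval for the contrast is 90.5–93.8%, against 95.0% with all data.

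**Step 4: wider assumptions** (4,000 trials per scenario; normal, t5, t3 or log-normal errors).

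- 1% per tail, complete data, ICC 0.3–0.7: contrast 6.2–10.2%, F 7.3–12.6%.
- 1% per tail, 20% of visits missing, ICC 0.5: contrast 6.6–10.3%, F 7.5–14.0%.
- 1% in total, complete data, ICC 0.5: contrast 5.7–7.4%, F 5.9–9.2%.
- 20% subject dropout, normal errors, ICC 0.63: contrast 7.1–10.9%, against 5.7% with all data.

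**Step 5: two-visit outcomes, one value per visit (80 values).** The (n+1)p definition gives 81 × 0.01 = 0.81, below 1, so nothing is deleted. Linear interpolation gives 79 × 0.01 = 0.79, so one goes per tail. Across the nine definitions 0, 1 or 2 values go. The error rate is 4.9–5.1% where none is deleted and 7.1–10.1% where two are.

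**Step 6: effect size.** If the contrast is divided by the model's total SD (the plan does not name a denominator), that SD falls from 1.00 to 0.93–0.98. The chance that a null effect exceeds .30 rises from 13.9% to 15.7–17.2% at ICC 0.63, or from 17.6% to 20.1–21.5% at ICC 0.5.

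**The case against.** The wording does not strictly define a cut-off, so the size of the inflation follows from a chosen reading. It is smallest with skewed or heavy-tailed data, where an outlier rule is most likely to be wanted. One run of 1,500 trials with log-normal errors and 1% in total gave 5.3% for the contrast, hard to separate from 5%. This is also a 40-person feasibility trial: no decision rule uses a p-value, and effect sizes are judged against .20 and .30. A rule stated in advance, without reference to arm, gives some protection against ad hoc deletion. Defining it and adding one all-data sensitivity analysis would cure most of the problem.

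Much of this stands as a limit on size. It does not remove the defect. The direction is the same on every percentile reading of the four-visit outcomes and, more weakly, for standardized cut-offs. Section 5.1 does plan between-group tests.

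A reader might infer three stronger claims that the documents do not support.

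- *The rule breaks the intent-to-treat commitment.* Section 5.1 defines that commitment by subjects, and with four complete visits no simulated trial lost a subject under the percentile rule. Dropping observed outcomes for poor fit is in tension with it, not a contradiction. A subject can leave the model entirely when visits are missing.
- *The rule erases strong responders.* Clear shrinkage (0.64 to 0.46) needed an invented extreme case, a quarter of the I-CAT arm gaining 2.6 SD. With a shared gain of 0.30 or 0.65 the estimate moved by less than 0.005.
- *All primary outcomes are affected alike.* DSI is absent from the mid-treatment and follow-up lists under Study Phases in the Synopsis, but present in Section 4.2.3 and in the Synopsis efficacy text. It counts as four-visit only if the latter govern. For cortisol, Section 2.1 describes "collecting saliva at 5 times points over 2.5 hours" but names no summary measure, so the number of modelled values is unknown.

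**Conclusion.** The concern holds for mDES, QLS, FESFS and PSS, and for DSI if it is collected at all four visits. Followed as written and read as a percentile rule, Section 5.1 raises nominal 5% error to roughly 5.5–11% for the baseline-to-post-treatment contrast and 6–14% for the interaction F test over the assumed range of inputs. The narrower 6–9.5% and 7–13% apply only to normal errors, complete data and ICC 0.5–0.63. Inflation is smaller for 1% in total, skewed errors or standardized cut-offs. For two-visit outcomes with one value per visit it runs from none to a similar size, depending on the percentile definition.

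These ranges rest on assumptions the documents do not supply: ICC, error shape, residual type, missingness and a single refit. One might infer that the treatment effect itself is biased; with no effect or a shared effect it essentially is not. The harm is false precision in the intervals and tests, and possibly in the standardized effect sizes. It is modest for a feasibility trial but avoidable, and should be corrected before analysis.

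**What to change.** Remove the residual-based exclusion from the primary analysis and keep every observed value. Exclude a value only if it is verified as a recording, device, assay or entry error, with the decision made blind to arm before the models are run. If residual trimming is still wanted, report it as a sensitivity analysis. State its cut-off (per tail or in total), percentile definition and residual type, and the numbers of observations and subjects removed in each arm. Reconcile the DSI visit schedule between the Synopsis and Section 4.2.3 so that its model is fixed.

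The cost is one or two sentences of SAP text, with no extra data or patients. Nominal standard errors rise by about 1–8% with normal errors (four visits, ICC 0.63: 0.271/0.268 = 1.01 to 0.271/0.250 = 1.08), which removes false precision. With strongly skewed errors the all-data estimate is slightly noisier: SD 0.271 against 0.260 for log-normal errors with four values deleted on conditional residuals.

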5.2 POWER ANALYSIS

We conducted a power analysis using the Optimal Design power software developed by Raudenbush. The results suggest that, with 20 subjects per group, $\alpha = .05$, and covariates that account for 40% of the variance, the study should have reasonable power ($B = .70$) to reliably detect treatment effect sizes of .65 or larger (although in this proposal, we have not designed the study with the anticipation that we will see effect sizes of this magnitude). We will compute effect sizes from these analyses and regard them as clinically meaningful if they exceed .20 for more distal outcomes and .30 for more proximal outcomes.

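### The stated power (.70 at an effect of .65) assumes covariates explaining 40% of variance, but the section 5.1 model contains none, so the figure does not describe the planned analysis

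*Combined protocol and SAP*

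**What the plan says.** Sections 2.1 (Sample Size Justification) and 5.2 carry the same power statement. In section 5.2 it is conditional: "covariates that account for 40% of the variance, the study should have reasonable power ($B = .70$) to reliably detect treatment effect sizes of .65". Section 2.1 gives the same inputs, "with 20 subjects per group, $\alpha=.05$, and covariates that account for 40% of the variance". Neither section names the covariates or says where the 40% comes from. Neither says whether .65 is in standard deviations of the outcome or of the change, or which visit or average it refers to. There is no attrition allowance.

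Section 5.1 describes the analysis: "The linear mixed-effects models will include effects of time (i.e., baseline, mid-treatment, post-treatment, and follow-up), intervention group", an interaction (printed as group by intervention, read here as group by time) and "random intercepts to account for baseline differences on outcome variables". The estimates follow from it: "Changes from baseline will be estimated using least-squares means for each intervention group". The synopsis describes the same approach, "hierarchical linear models with random intercepts for each subject that will estimate the average change from baseline" for each group. No covariate appears in either place. Section 2.2 lists demographic and clinical variables, but only as possible covariates.

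The analysis is by intention to treat, "in which all subjects randomized will be included in the analysis".

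**The concern.** The power figure and the analysis model describe two different analyses. The power figure takes credit for covariates that remove 40% of the outcome variance. The model has no term that does this. A random intercept is not a substitute. With baseline as a response level and a free group effect, the group-by-time term compares mean changes, and the variance of a change depends on the correlation between visits.

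A reader of section 5.2 therefore cannot tell what sensitivity the planned comparison has. The gap also bears on the trial's stated goal in section 2.1, which is to estimate effect sizes for a larger trial. A free baseline difference discards information that has already been collected and widens every interval. Repeated visits cannot make this up for cortisol, which section 2.1 calls the primary outcome measure. The synopsis defines that outcome as "Least means change from baseline to post-treatment on salivary cortisol", and heart rate variability follows the same two-visit schedule. The Daily Stress Inventory would be in the same position if the synopsis schedule governs rather than section 4.2.3.

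**Working it through.** **Inputs from the documents:** 20 per group, alpha .05, covariate R² 0.40, effect .65, stated power .70.

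**Assumptions:** two-sided test; effect in SDs of the outcome (SD = 1); equal variances and a common correlation ρ between visits, taken over 0.3 to 0.8; loss rates as shown. Power is from the noncentral t distribution with noncentrality 0.65 / √(f × 2/20), where f is the residual variance factor. There are 38 degrees of freedom, or 37 with a covariate.

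**1. The plan's own figure.** f = 1 − 0.40 = 0.60. The standard error is √(0.60 × 2/20) = 0.245, the noncentrality is 0.65/0.245 = 2.65, and power is 0.73. The effect detectable with power .70 is 0.625. The stated .70 at .65 is thus slightly conservative if the covariates exist. With no covariate and a single-time comparison, f = 1 and power is 0.52.

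**2. The model in section 5.1, one-visit contrast.** With complete data the estimate is the difference in mean change, and f = 2(1 − ρ).

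**3. The same data with a common baseline mean** (or baseline as a covariate). Here f = 1 − ρ².

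| ρ | f, as written | Power | f, baseline-adjusted | Power | Width ratio √(2/(1+ρ)) |
|---|---|---|---|---|---|
| 0.3 | 1.400 | 0.39 | 0.910 | 0.56 | 1.24 |
| 0.5 | 1.000 | 0.52 | 0.750 | 0.64 | 1.15 |
| 0.63 | 0.735 | 0.65 | 0.600 | 0.73 | 1.11 |
| 0.7 | 0.600 | 0.73 | 0.510 | 0.80 | 1.08 |
| 0.8 | 0.400 | 0.89 | 0.360 | 0.92 | 1.05 |

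The row at 0.63 matters because √0.40 = 0.632 is the correlation at which the baseline score alone would explain 40%. If that was the intention, the written model gives 0.65 and baseline adjustment gives 0.73. Power of .70 needs ρ of about 0.67 as written and about 0.59 with adjustment. Simulated trials fitted by REML with a random intercept agree: at ρ = 0.63, two visits, 0.644 as written and 0.740 with a common baseline mean.

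**4. Other readings.** If .65 is in SDs of change, f = 1 and power is 0.52 at every ρ. For the average of three post-baseline visits with a free baseline difference, f = (4/3)(1 − ρ). Power is then 0.69 at ρ = 0.5 and 0.82 at 0.63.

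**5. Attrition, two visits.** With a common baseline mean and all baselines kept, f = (1 − ρ²)/(1 − loss).
- ρ = 0.63: 0.71 at 5% loss, 0.69 at 10%, 0.63 at 20%.
- ρ = 0.5: 0.64 with no loss, 0.59 at 10%, 0.54 at 20%.
- As written, ρ = 0.63 and 20% loss, likelihood estimation: f = 0.60/0.80 + (1 − 0.632)² = 0.885, power 0.56.

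**6. Precision at ρ = 0.5.** The 95% half-width is 2.024 × √(1.00 × 2/20) = 0.64 SD as written, and 2.026 × √(0.75 × 2/20) = 0.55 SD with adjustment. The plan's thresholds for a clinically meaningful effect are .20 and .30.

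**The case against.** The strongest reply is that little rests on this number. Sections 2.1 and 5.2 say that the study was not designed in the expectation of effects as large as .65. The sample size is supported by recruitment capacity, and the aim is feasibility and effect-size estimation. There is no arithmetic error, and a mixed model with a free baseline difference is a valid analysis of change in a randomized trial. All of this stands, and it is why the consequence is modest.

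Two technical points also stand in part. Using the roughly 114 residual degrees of freedom of the four-visit model raises one-visit power by about 0.01 to 0.015, and moves the three-visit average at ρ = 0.5 from 0.69 to 0.70. This does not change the picture, and section 5.1 names no averaged contrast as the test. The software settings are not given, so the original calculation cannot be seen; step 1 assumes an ordinary covariate-adjusted comparison.

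A common baseline mean is justified when baseline is measured before randomization. The order of visits fits this, but no section says so, and the plan should. Section 4.1.2 is partly in the past tense, which might mean that the trial was already running; that is not proof. Covariates are foreseen in section 2.2, but a list for possible use does not put them into the model.

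**Conclusion.** The point holds. The stated power belongs to an analysis with covariates explaining 40% of the variance, and section 5.1 specifies a different one. The figure is unsupported rather than wrong: power for the written one-visit contrast is 0.39 to 0.89 for ρ from 0.3 to 0.8, on either side of .70. These values assume a two-sided .05 test, an effect in outcome SDs and no loss; ρ is not in the documents.

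The practical loss is precision. Intervals for a one-visit contrast, the only kind available for cortisol and heart rate variability, are 24% wider than with baseline adjustment at ρ = 0.3 and 5% wider at 0.8. At ρ = 0.5 neither version resolves the .20 and .30 thresholds, so the plan should say what precision it can deliver. The change should be made, but the trial's feasibility aims do not depend on it.

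**What to change.** In section 5.1, adjust each efficacy outcome for its baseline value. The preferred form keeps baseline as a response level and constrains the groups to a common mean there: time effects, plus group-by-time effects at the post-baseline visits only. State that baseline is measured before randomization. This matches the precision of a baseline covariate, keeps every randomized subject in the model, and still gives least-squares mean changes by group.

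Restate sections 2.1 and 5.2 for that model, naming the visit or average and the SD in which the effect is expressed. For example: *One-visit contrast, 20 per group, two-sided .05, effect .65 outcome SDs. Assumed correlation 0.63 (R² 0.40): power about 0.73 with no loss, 0.69 with 10% and 0.63 with 20% loss. Assumed correlation 0.5: 0.64, 0.59 and 0.54.* Add the expected 95% half-width.

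If the section 5.1 model stays as it is, either name the covariates expected to explain 40% of the variance and put them in the model, or restate power for the change contrast over stated ranges of ρ and attrition.

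The cost is one model sentence in section 5.1 and revised text in sections 2.1 and 5.2. Baseline values are already collected, and no patients or visits are added. If the trial is already under way, date and record the change as an amendment.

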behavioral therapy (CBT), and cognitive remediation are aimed at improving the proximal deficits surrounding symptoms, relapse, and cognitive impairments, but these treatments often have only small to moderate effects on long-term functional recovery (Dixon et al., 2010). None of these interventions directly address impaired stress reactivity that we theorize is an underlying deficit strongly associated with relapse risk and impaired functional recovery. There is thus a critical need for a shift in the design and application of treatments for schizophrenia to more adequately address the lack of functional recovery and high relapse risk. The research proposed in this application is innovative because it represents a departure from the status quo of the current array of treatments and targets functional recovery and relapse prevention through an intervention aimed at improving resilience to stress. There are a number of proximal measures associated with stress reactivity including autonomic, endocrine, and immune system function measures that will be key indicators of treatment change in this paradigm shift. We propose to test this theory targeting stress reactivity by developing an intervention aimed at altering the stress response through mindfulness, as well as buffering against the negative effects of stress through meaningful coping strategies and positive affect. This should restore allostatic load and result in functional recovery (Bower et al., 2008; Hamilton et al., 2006; Mauss et al., 2011).

[figure not shown]

Figure 1. A pilot study of 10 schizophrenia (SCZ) probands, and 17 controls (CTL), aged 19.4 ± 3.5 , using the Montreal Imaging Stress Task (MST) was done in a laboratory setting (not in the scanner). Compared to CTLs, SCZ probands had abnormal reactivity to the 20-minute stressor (shaded area). CTLs showed the expected rise and fall of cortisol, decreased parasympathetic activity, and minimally increased sympathetic activity, with complete recovery following stressor termination. Patients showed blunted cortisol and parasympathetic responses and elevated, prolonged sympathetic reactivity.

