3.1 OUTCOMES

The central hypothesis is that I-CAT will increase positive emotions, increase role functioning, and decrease stress reactivity as measured by self-report measures and salivary cortisol. Secondary hypotheses are that I-CAT will decrease psychiatric symptoms, increase mindfulness, and increase well-being as measured by self-report, clinical interview measures, and heart rate variability. Guided by strong preliminary data, this hypothesis will be tested via four specific aims:

1. To examine the feasibility of implementing I-CAT at a community mental health clinic
2. To examine the tolerability of I-CAT at a community mental health clinic
3. To examine I-CAT adherence through attrition and attendance rates
4. We will also examine the impact of I-CAT on primary outcomes (positive emotions, role functioning, stress reactivity), and secondary outcomes (psychiatric symptoms, mindfulness, well-being) compared with TAU.

We hypothesize that I-CAT will be associated with:

- Improved primary outcomes including increased positive emotions, increased role functioning, and decreased stress reactivity at mid-point, post-test, and three-month follow-up.

- Improved secondary outcomes including decreased psychiatric symptoms, increased mindfulness, and increased well-being at mid-point, post-test, and three-month follow-up.

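### Effects are to be called clinically meaningful when the point estimate alone passes .20 or .30, but at 20 per arm the 95% CI half-width (about 0.40 to 0.76 SD for change from baseline) exceeds both cut-offs

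*Combined protocol and SAP*

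**What the plan says.** The same rule appears in the Sample Size Justification paragraph of section 2.1 and again in section 5.2: effect sizes will be computed, and the team will "regard them as clinically meaningful if they exceed .20 for more distal outcomes and .30 for more proximal outcomes". Nothing else is required for the label.

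The effects come from the mixed model in section 5.1: "Changes from baseline will be estimated using least-squares means for each intervention group". That section also sets out to test whether the arms differ in their change over time, but the label is not tied to that test, and no confidence interval is mentioned. The Synopsis (Efficacy Evaluations) likewise defines outcomes as change, for example "Least means change from baseline to post-treatment on salivary cortisol". For the psychological outcomes, section 3.1 expects "increased positive emotions, increased role functioning, and decreased stress reactivity at mid-point, post-test, and three-month follow-up".

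On purpose, section 2.1 says the trial is meant "to estimate effect sizes in preparation for a larger clinical trial" and that "comparing I-CAT to an active treatment will establish an accurate estimate of effect size from our key outcome domains". The same section also says that completing this stage "will provide preliminary information on the possible impact of I-CAT on stress reactivity".

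Neither section 2.1 nor section 5.2 says what the effect size is divided by, or lists which outcomes count as distal and which as proximal.

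**The concern.** A cut-off on a point estimate is informative only if the estimate is reasonably precise relative to that cut-off. With 40 participants it is not. Followed as written, the rule lets the report call an effect clinically meaningful when its 95% interval includes no effect and some harm. The estimates are intended to feed a larger trial, so its planners could take a label in place of the uncertainty they need to see. The word *accurate* in section 2.1 adds to that risk.

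**Working it through.** **Inputs from the documents.** 20 per arm (sections 2.1 and 5.2); alpha .05 (section 5.2; two-sided assumed, since sidedness is not stated); covariates explaining 40% of variance (section 5.2); cut-offs .20 and .30 (section 5.2). The model in section 5.1 lists no covariates, so R² = 0 is the other bound.

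**Assumptions, not in the documents.** All 20 per arm observed; equal variances over time; within-subject correlation ρ between baseline and the later visit from .3 to .8; effects signed so that positive favours I-CAT.

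**The plan's own figure.** Section 5.2 gives power .70 for an effect of .65. The standard error is √(0.6 × 2/20) = 0.245 and the noncentrality is .65/0.245 = 2.65. A two-sided t-test on 38 df then gives power 0.734, and the effect detectable at 70% power is 0.625. The stated figure is not reproduced exactly but is slightly conservative. This does not affect the point, because the interval width depends only on n, the confidence level and the residual variance.

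**Formulas.**
- Single-visit contrast, in outcome SDs: SE = √((1 − R²) × 2/20).
- Change from baseline, in baseline SDs: SE = √(2(1 − ρ) × 2/20).
- 95% half-width = 2.024 × SE (t on 38 df).
- Chance of the label with no true effect, one outcome at one visit: P(Z > cut-off/SE).

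| Contrast | SE | Half-width | Label rate at .20 | Label rate at .30 |
|---|---|---|---|---|
| Single visit, R² = 0 | 0.316 | 0.640 | 26.4% | 17.1% |
| Single visit, R² = .40 | 0.245 | 0.496 | 20.7% | 11.0% |
| Change, ρ = .3 | 0.374 | 0.757 | 29.7% | 21.1% |
| Change, ρ = .5 | 0.316 | 0.640 | 26.4% | 17.1% |
| Change, ρ = .7 | 0.245 | 0.496 | 20.7% | 11.0% |
| Change, ρ = .8 | 0.200 | 0.405 | 15.9% | 6.7% |

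**Which rows apply.** The Synopsis and section 5.1 estimate change from baseline, so the change rows match the planned analysis. That includes cortisol, whose outcome is change to post-treatment.

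**Intervals at the cut-offs.**
- R² = 0: an estimate of .20 has a 95% CI of −0.44 to 0.84, and one of .30 has −0.34 to 0.94.
- R² = .40: −0.30 to 0.70 and −0.20 to 0.80.
- Change at ρ = .8, the most favourable case tried: −0.20 to 0.60 and −0.10 to 0.70.

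All include zero. On the change scale an estimate must reach 0.40 (ρ = .8) to 0.76 (ρ = .3) before its interval excludes zero.

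**Sensitivity.**
- Multiplier 1.96 instead of 2.024: the change half-widths become 0.39 to 0.73.
- Dividing by the SD of change: the SE is √(2/20) = 0.316 whatever ρ is, so the half-width is 0.64.
- For the half-width to fall to .30, R² would have to be 1 − 10 × (.30/2.024)² = 0.78; for .20, 1 − 10 × (.20/2.024)² = 0.90. The plan assumes .40.
- Dropout widens the interval. With 16 per arm observed (illustrative), the 1.96-based single-visit half-width is 0.54 to 0.69, against 0.48 to 0.62 with 20.

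**The case against.** The best defence is that this is a feasibility trial. It defines feasibility by recruitment, engagement, attrition and feedback, states modest power openly, says it does not expect effects as large as .65, and calls its impact information preliminary. Benchmarks of magnitude and tests of significance answer different questions, and .20 and .30 may be reasonable as the former. All of that stands, and it is why the remedy is wording rather than sample size. It does not rescue a rule that attaches *clinically meaningful* to an estimate whose interval includes zero and harm.

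Several stronger readings are tempting but not supported:

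- **That cortisol and heart rate variability are already assigned to the .30 cut-off.** Section 1 does say "There are a number of proximal measures associated with stress reactivity including autonomic, endocrine, and immune system function measures". But that section is background and does not mention the cut-offs. It also uses the word proximal for deficits around symptoms, relapse and cognition. It assigns no outcome to either cut-off.
- **That the promise of accuracy is simply false.** The sentence in section 2.1 partly justifies an active comparator, which is a matter of validity. The wording is loose and sits badly beside the same section's *preliminary information*, but it is not purely a claim about precision.
- **That visits or cut-offs will be picked after the results are seen, or intervals withheld.** The documents suggest neither. Section 3.1 names all three visits, and the natural reading is that the benchmark applies at each. The missing proximal/distal list is missing detail.
- **That the label decides whether a larger trial goes ahead.** No such rule is stated.

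**Conclusion.** The point holds as a reporting defect that should be corrected; it does not threaten the validity of the trial. At 20 per arm the 95% half-width exceeds both cut-offs under every assumption tried: 0.64 SD with no covariates, 0.50 SD with R² = .40, and 0.40 to 0.76 baseline SD for the planned change contrast. With no true effect, a single comparison would be labelled meaningful in 16-30% of trials at .20 and 7-21% at .30 on the change scale, cortisol included, or in 21-26% and 11-17% for a single-visit contrast.

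The change-scale figures rest on assumed correlations of .3 to .8, equal variances and complete data. The exact values move with these and with the undefined divisor of the effect size; the conclusion does not change anywhere in the range.

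**What to change.** In sections 2.1 (Sample Size Justification) and 5.2, replace the rule with:

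> Each effect size (between-group difference in change from baseline divided by the pooled baseline SD) will be reported with its 95% CI. The .20 and .30 values are benchmarks of magnitude only. No effect will be called clinically meaningful on its point estimate alone; we will state whether the interval includes zero and whether it includes the benchmark.

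Next to it, state the expected half-width and its assumptions: all 20 per arm observed; 0.40 to 0.76 baseline SD for change from baseline at within-subject correlations of .8 to .3; and, for a single-visit contrast, 0.64 SD without covariates or 0.50 SD if covariates explain 40% of variance.

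In section 2.1 (Justification and Feasibility), replace *accurate estimate* with *preliminary estimate*.

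As a secondary clarification, list each outcome as proximal or distal before analysis, cortisol and heart rate variability included.

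The cost is a few sentences, a short list and interval reporting, with no new data. The downside is that fewer effects will be described as meaningful.
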